3.3.4.2 Withdrawal of consent to trial participation

Patients may withdraw their consent to trial participation at any time without the need to justify the decision.

If a patient wants to withdraw consent, the investigator should be involved in the discussion with the patient and explain the difference between trial treatment discontinuation and withdrawal of consent to trial participation, as well as explain the options for continued follow-up after trial treatment discontinuation, please see [section 6.2.4](#).

3.3.4.3 Discontinuation of the trial by the sponsor

Boehringer Ingelheim reserves the right to discontinue the trial overall or at a particular trial site at any time for the following reasons:

Failure to meet expected enrolment goals overall or at a particular trial site.

New efficacy or safety information invalidating the earlier positive benefit-risk-assessment, please see [section 3.3.4.1](#).

Deviations from GCP, the trial protocol, or the contract impairing the appropriate conduct of the trial.

Further follow up of patients affected will occur as described in [section 6.2.4](#).

The investigator / the trial site will be reimbursed for reasonable expenses incurred in case of trial termination (except in case of the third reason).

4. TREATMENTS

4.1 INVESTIGATIONAL TREATMENTS

The trial medication (BI 685509 and matching placebo) will be provided by Boehringer Ingelheim.

4.1.1 Identity of the Investigational Medicinal Products

The characteristics of the Investigational Medicinal Products are described in [Table 4.1.1: 1 to 6](#).

Table 4.1.1: 1 BI 685509 1 mg

Substance:	BI 685509
Pharmaceutical formulation:	Film-coated tablets
Source:	Boehringer Ingelheim Pharma GmbH & Co. KG
Unit strength:	1 mg
Posology:	TID
Method and route of administration:	Oral (p.o)

Table 4.1.1: 2 BI 685509 2 mg

Substance:	BI 685509
Pharmaceutical formulation:	Film-coated tablets
Source:	Boehringer Ingelheim Pharma GmbH & Co. KG
Unit strength:	2 mg
Posology:	TID
Method and route of administration:	Oral (p.o)

Table 4.1.1: 3 BI 685509 3 mg

Substance:	BI 685509
Pharmaceutical formulation:	Film-coated tablets
Source:	Boehringer Ingelheim Pharma GmbH & Co. KG
Unit strength:	3 mg
Posology:	TID
Method and route of administration:	Oral (p.o)

Table 4.1.1: 4 Placebo matching BI 685509 1 mg

Substance:	Placebo to BI 685509 film-coated tablets 1 mg
Pharmaceutical formulation:	Film-coated tablets
Source:	Boehringer Ingelheim Pharma GmbH & Co. KG
Unit strength:	Not applicable
Posology:	TID
Method and route of administration:	Oral (p.o)

Table 4.1.1: 5 Placebo matching BI 685509 2 mg

Substance:	Placebo to BI 685509 film-coated tablets 2 mg
Pharmaceutical formulation:	Film-coated tablets
Source:	Boehringer Ingelheim Pharma GmbH & Co. KG
Unit strength:	Not applicable
Posology:	TID
Method and route of administration:	Oral (p.o)

Table 4.1.1: 6 Placebo matching BI 685509 3 mg

Substance:	Placebo to BI 685509 film-coated tablets 3 mg
Pharmaceutical formulation:	Film-coated tablets
Source:	Boehringer Ingelheim Pharma GmbH & Co. KG
Unit strength:	Not applicable
Posology:	TID
Method and route of administration:	Oral (p.o)

4.1.2 Selection of doses in the trial and dose modifications

The target doses of BI 685509 used for this trial will be 1 mg TID, 2 mg TID and 3 mg TID. These doses were selected based on the safety and PK results of the 1366-0004 phase I MRD trial.

In healthy volunteer phase I trials doses starting with 0.5 mg QD were tested. At 1 mg TID the first signal of slight pharmacodynamic (PD) effects on blood pressure and heart rate was seen. Doses higher than 3 mg TID were not well tolerated.

4.1.3 Method of assigning patients to treatment groups

After the assessment of all in- and exclusion criteria at Visit 3, each eligible patient will be randomised according to a randomisation plan.

Table 4.1.3: 1 Dose Groups and Treatments

	Target dose starting Visit 5	Randomisation ratio	Patients to be enrolled
Dose Group 1	1 mg BI 685509 TID	3	60
	Placebo matching 1 mg BI 685509 TID	1	20
Dose Group 2	2 mg BI 685509 TID	3	60
	Placebo matching 2 mg BI 685509 TID	1	20
Dose Group 3	3 mg BI 685509 TID	3	60
	Placebo matching 3 mg BI 685509 TID	1	20

Randomisation codes will be generated through a validated software and kept blinded to the trial team, sites and patients. An Interactive Response Technology (IRT) system will be used to screen patients, perform drug assignment, manage initial/ re-supply ordering of drug supplies and handle emergency un-blinding.

The investigator will receive all necessary instructions from the sponsor to access the IRT. Detailed IRT functions and procedures will be documented in the User Requirement Specifications mutually agreed by the sponsor and the IRT vendor. Note that the medication number is different from the patient number (the latter is generated during screening via the IRT System).

4.1.4 Drug assignment and administration of doses for each patient

All patients, regardless of dose group assigned, will start on a dose of 1 mg TID of BI 685509 or matching placebo. Up-titration or pseudo up-titration will occur after 14 days and after 28 days in each dose group, until the maximum planned dose for that dose group is reached. Patients who do not tolerate an up-titration, e.g., due to orthostatic dysregulation, should follow the guidance in [section 4.1.4.2](#).

The treatment assignments and dose regimen are detailed in [Table 4.1.4: 1](#).

Table 4.1.4: 1 Treatment assignments and dose regimen

Randomisation Allocation	Weeks 1 & 2	Weeks 3 & 4	Weeks 5 to 20
	Dispensed at Visit 3	Dispensed at Visit 4	Dispensed at Visits 5, 6,7 & 8
Dose Group 1	1 mg BI 685509 or matching placebo TID	1 mg BI 685509 or matching placebo TID	1 mg BI 685509 or matching placebo TID
Dose Group 2	1 mg BI 685509 or matching placebo TID	2 mg BI 685509 or matching placebo TID	2 mg BI 685509 or matching placebo TID
Dose Group 3	1 mg BI 685509 or matching placebo TID	2 mg BI 685509 or matching placebo TID	3 mg BI 685509 or matching placebo TID

It is recommended that the first daily dose is taken in the morning, the middle dose around lunchtime, and the third dose in the evening (one tablet at each time point). There must be at least 4 hours in between trial medication intake. If a dose is missed this should not be rectified by taking two doses at the next time point. The medication should be taken with a glass of water and can be taken with or without food. The last dose of trial medication will be administered in the evening of the day before the EoT visit.

All trial medication assignments including up/down-titrations and replacement kits will be managed through the IRT system. Standard up-titrations in the first 4 weeks have to be done in the same manner for all patients to blind the patient to the dose group they're assigned to. If no true up-titration is required for a patient at regular timepoints (i.e. Visit 4 and again at Visit 5), then the patient will still get new medication on the same dose as before. All patients will be told that the medication could either be the same or a higher dose depending on the treatment and dose group to which the patient is allocated.

During a COVID-19 or similar pandemic, physical visits to the sites may need to be restricted to ensure patient safety. Based on a thorough assessment of the benefits and risks, the investigator may still decide to continue the trial treatment and trial medication may be shipped to the patient's home if acceptable according to local law and regulations (for more details see [section 6.2.1](#)). Shipment of trial medication to the patient's home will also be allowed to support regular visits performed at the patient's home.

Potential down-titrations (dose reductions) can be done based on the dose group known by the investigational site. This will be managed via the IRT system. Dose reductions must not be performed by instructing the patient to take less than the three daily doses. While the patient will not get to know the precise rules as listed in [sections 4.1.4.1](#) and [4.1.4.2](#), the patient will be informed that down-titrations may be needed as decided by the investigator.

4.1.4.1 Rules for titration in case of interruption of trial treatment

Since an interruption of trial medication may have an influence on the tolerance, the following rules will apply for the safety of the patient:

An interruption of trial treatment is defined as any occurrence where 4 consecutive doses* or more were not administered (i.e. missed or dosing temporarily discontinued). **One dose refers to an individual timepoint e.g. morning dose, or middle dose or evening dose.*

- If less than 4 consecutive doses of trial medication are missed then the next dose of trial medication should be taken as scheduled.

After an interruption of trial treatment the patient should be restarted at 1 mg BI 685509/ placebo TID independent from the dose the patient was on before unless the patient was down-titrated due to an adverse event (see [section 4.1.4.2](#)) in which case:

- If they had been on 2 mg/3 mg BI 685509/ placebo they would re-start on 1 mg BI 685509/ placebo.
- If they had been on 1 mg BI 685509/ placebo then they should restart on placebo (matching 1 mg BI 685509).

Before any up-titration occurs the patient must have taken the preceding dose for at least 7 consecutive days. This applies throughout the treatment period.

- This may mean that a patient due to be up-titrated at Visit 4 or 5 (as per [Table 4.1.4: 1](#)) is held at their current dose until their next scheduled visit. They could also be up-titrated at an unscheduled visit once this requirement is met.

If interruption for any reason occurs after Visit 5, subsequent up-titration will be allowed either at a scheduled or unscheduled visits.

Patients with an interruption on 2 mg or 3 mg or matching placebo will need to return to the clinic either for the next scheduled or an unscheduled visit to receive 1 mg tablets before continuation of trial treatment.

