However, in case the patient experiences a related adverse event or for any other reason the patient pauses trial treatment, the investigator will need to decide whether a down-titration is needed based on the rules reflected in [section 4.1.4](#) and the dose group the patient is assigned to. The patient will not know the specific rules. This will eliminate an additional burden of the patient to visit the site for a sham-downtitration if the patient is staying on the lowest dose already.

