4.1.4.2 Rules for down-titration in case of intolerance to trial treatment

If a patient has an adverse event that the Investigator believes may be related to trial medication then the Investigator may either interrupt a patient's trial medication (re-start to follow the rules above (see [section 4.1.4.1](#)) or dose reduce the patient as described below. See [Appendix 10.3](#) for a schematic guidance on down-titration:

If the patient is on 1 mg TID or matching placebo the patient will be down-titrated to placebo matching 1 mg.

If the patient is on 2 mg TID or 3 mg TID (or corresponding matching placebo) and interrupts trial treatment

- less than 4 consecutive doses, then the patient will be down-titrated one level i.e.
 - 2 mg /placebo goes to 1 mg TID/ placebo.
 - 3 mg/ placebo goes to 2 mg TID/ placebo.
- 4 consecutive doses or more, then the patient will be down-titrated to 1 mg TID or placebo.

Dose-reduction must NOT be performed by taking less than the three daily doses or by splitting tablets so that a whole tablet isn't taken.

If the patient experiences a second adverse event that the Investigator believes is related and they have already had an interruption/ down-titration, then the patient should permanently discontinue trial treatment.

In case of persistent adverse events despite dose reduction, or severe effects at any dose, permanent treatment discontinuation should be considered.

Uptitration for patients who were down-titrated or interrupted for a related AE is not permitted.

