5. ENDPOINTS

5.1 PRIMARY ENDPOINT(S)

Please refer to the protocol.

The three different approaches for handling intercurrent events (ICEs) are summarised in the table below:

Estimand strategy name	Treatment	ICE handling
Primary approach	Randomised treatment	Study med d/c: include data prior to study med d/c. Death: include data prior to death. SGLT2i initiation/discontinuation: include data prior to SGLT2i start/stop.
Supplementary 1	Randomised treatment	Study med d/c: include all available data. Death: include data prior to death. SGLT2i initiation/discontinuation: include all available data.
Supplementary 2	Actual final treatment	Study med d/c: include data prior to study med d/c. Death: include data prior to death. SGLT2i initiation/discontinuation: include data prior to SGLT2i start/stop.

SGLT2i = Sodium-Glucose co-Transporter-2 Inhibitor

Note that the table above should be used along with [Table 6.6.2.1:1](#) to derive endpoints for primary, supplementary 1, and supplementary 2 analysis.

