6.6.2 Efficacy data

6.6.2.1 Primary endpoint

Missing data for primary analysis will not be imputed:

- If some UACR value(s) for UACR at baseline is (/are) missing, all available UACR samples in week -2, -1, and 0 will be used to derive UACR at baseline.
- If any UACR value after randomisation is missing, the missing UACR will not be imputed; missing UACR due to ICEs will not be imputed.

The Mixed-effect Model for Repeated Measures (MMRM) approach used for the primary analysis (see [Section 7.4.1](#)) allows for missing data, assuming the missing data mechanism is ignorable. Even patients with only one post-baseline assessment can be included in the model and can, therefore, participate in variance estimation. The statistical model assumes that patients who had an ICE would have behaved similarly to those who remained in the study. The table below describes how/when to derive UACR values for MMRM:

Table 6.6.2.1: 1 Principal rule of UACR derivation for MMRM

UACRs for MMRM	UACR at baseline	UACR at visit 6	UACR at visit 7	UACR at EoT
Visits need to be included	First Morning Void (FMV) or 10-hour urine UACR baseline is defined as the mean of all non-missing assessments from Visit 2 until prior to the first intake of trial medication.	All available scheduled visits at visit 6	All available scheduled visits at visit 7	All available scheduled visits between visit 8 and EoT
Derivation	Average of all available UACR measurements defined at each visit			

Note: all available/scheduled UACR measurements will be used: no imputation for missing UACR measurement; this rule will be applied to FMV and 10-hour urine samples, respectively.

Sensitivity analyses will be conducted to investigate the potential effect of ICE handling approaches on the results of the primary analysis. Details about implementation of the sensitivity statistical analyses are described in [Section 7.4](#).

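### Protocol 4.1.4.1 and 4.1.4.2 give opposite up-titration rules for a patient who restarts after interrupting treatment for a related adverse event after Visit 5

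*Protocol*

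**What the plan says.** Section 4.1.4.1 of the protocol defines an interruption as four or more consecutive doses not given, including doses temporarily withheld. The definition has no exception for adverse events. A patient who restarts does so at 1 mg TID or placebo, with a separate restart dose that applies "unless the patient was down-titrated due to an adverse event". Two sentences in this section govern later increases:

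- "Before any up-titration occurs the patient must have taken the preceding dose for at least 7 consecutive days"
- "If interruption for any reason occurs after Visit 5, subsequent up-titration will be allowed either at a scheduled or unscheduled visits"

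Section 4.1.4.2 covers adverse events that the investigator thinks may be related. The investigator may reduce the dose or interrupt the "trial medication (re-start to follow the rules above", that is, those of 4.1.4.1. For patients on 2 or 3 mg TID who miss four or more consecutive doses, it also sets 1 mg TID or placebo as the dose. It ends: "Uptitration for patients who were down-titrated or interrupted for a related AE is not permitted". That sentence has no limit by visit or time.

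On the analysis side, SAP Table 6.6.2.1: 1 builds the end-of-treatment UACR from "All available scheduled visits between visit 8 and EoT". The primary approach (Protocol 7.2.2, SAP 5.1) analyses patients as randomised, and temporary interruption is not among its intercurrent events. Supplementary 2 instead groups patients by "Actual final treatment".

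**The concern.** One sentence allows up-titration after an interruption whatever its cause. The other forbids it for one cause. Both are current text, not amendment history, and the second section sends the restart back to the first, so the same patient is subject to both.

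The main issue is patient safety. Protocol 3.3 expects about 100 sites, and under Protocol 3.2 investigators know the dose group. Two sites reading the same protocol could treat the same patient differently: one would raise the dose back towards the level at which the related event occurred, the other would not.

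The analysis consequence is secondary. The primary analysis keeps these patients in their randomised dose group whichever rule the site followed. The rule can also change their group in Supplementary 2.

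**Working it through.** **Comparing the two sections.** Take a patient on 2 or 3 mg TID (or matching placebo) who misses four or more doses for a related adverse event after Visit 5 and restarts.

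| Question | Section 4.1.4.1 | Section 4.1.4.2 |
|---|---|---|
| Does the section apply? | Yes, by its definition of interruption | Yes, related event |
| Restart dose | 1 mg TID or placebo | 1 mg TID or placebo |
| Later up-titration | Allowed, after 7 days on the preceding dose | Not permitted |
| States which section prevails? | No | No |

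Section 4.1.4.1 does make an exception for adverse events, but only for the restart dose of patients already down-titrated. It makes none for later increases. Neither the amendment log nor the rest of the visible protocol contains a sentence that settles the matter.

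**Who can be affected.** Real up-titration exists only in dose groups 2 and 3, planned at 2 × (60 + 20) = 160 of 240 patients, placebo included. The period after Visit 5 is weeks 5 to 20, or 16 of the 20 treatment weeks. The documents do not say how many patients would interrupt for a related event in that time.

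**Effect on the endpoint dose.** Inputs are nominal days from the flow charts:

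- Visit 5 is Day 29, Visit 8 is Day 127 and EoT is Day 141. The last dose is on Day 140.
- Urine is collected 2 and 1 days before Visit 8 (Days 125 and 126) and 8, 7, 2 and 1 days before EoT (Days 133, 134, 139 and 140), giving six samples.
- Restart days are counted from Day 31 to Day 140: 140 − 31 + 1 = 110 days.
- At 7 days per step, regaining the target takes at least 7 days in dose group 2 (1 to 2 mg) and 14 days in dose group 3 (1 to 2 to 3 mg).

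| | Dose group 2 | Dose group 3 |
|---|---|---|
| Latest restart with all six samples at target | 125 − 7 = Day 118 | 125 − 14 = Day 111 |
| Restart days from Day 31 | 118 − 31 + 1 = 88 | 111 − 31 + 1 = 81 |
| Share of 110 days | 80.0% | 73.6% |
| Latest restart with the last sample at target | 140 − 7 = Day 133 | 140 − 14 = Day 126 |

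Under the other rule, an actively treated patient stays at 1 mg TID (3 mg/day, against a target of 6 or 9 mg/day) until EoT. For restarts from Day 134 in dose group 2 or Day 127 in dose group 3, the target cannot be regained before the last sample under either rule.

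**Illustration for power.** Because no interruption rate is given, assume that a fraction f of the 6 and 9 mg arms stays at 3 mg/day and has only that dose's assumed effect. The planning effects of 0.20 and 0.35 in Protocol 7.5 become 0.20 − 0.10f and 0.35 − 0.25f. The other inputs are 60 patients per arm, one-sided 5% and the five candidate shapes. The SD of 0.681 is not in the documents; it was solved so that f = 0 returns the stated 88.5%.

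| f | Power |
|---|---|
| 0 | 88.5% |
| 1% | 88.1% |
| 2% | 87.7% |
| 3% | 87.2% |
| 5% | 86.3% |

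The loss is 0.4 to 2.2 points. For these fractions it is an upper bound on the difference between the rules, because it assumes full return to target, with full effect, under the other one.

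**The case against.** The best reply is that the sections can be read together. Section 4.1.4.1 is the general rule, 4.1.4.2 is the specific rule for intolerance, and a specific prohibition placed after a general permission is normally its exception. Otherwise the prohibition would have no effect on interruptions in weeks 5 to 20. The 4.1.4.1 sentence may also be meant only to settle the type of visit, since no titration visit is scheduled after Visit 5. The reference back in 4.1.4.2 concerns the restart, which is compatible with a separate up-titration rule. The exception in 4.1.4.1 itself points to 4.1.4.2.

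These are plausible accounts of intent, but the text does not state them. The 4.1.4.1 sentence grants permission and covers every cause. Its pointer to 4.1.4.2 concerns the restart dose after a down-titration, not increases after an interruption.

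Protocol 3.2 adds little to either side. It mentions a pause "in case the patient experiences a related adverse event or for any other reason the patient pauses trial treatment", but on the question of whether to down-titrate.

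Appendix 10.3 and the IRT specification cannot be seen here and may settle practice. They would not remove the conflict between the two sentences.

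Some limits on the concern stand. The affected group is narrow. A second related event after an interruption or down-titration leads to permanent discontinuation under 4.1.4.2, although that applies only once it has happened. The 80% and 74% are shares of calendar days, not of patients.

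**Conclusion.** The concern holds. For related-event interruptions of four or more doses after Visit 5 in dose groups 2 and 3, the protocol both allows and forbids later up-titration. For interruptions with other causes the sections do not conflict on this point, and in dose group 1 the conflict has little practical effect.

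The weight rests on patient safety: conflicting dosing instructions after a drug-related event should not be left to site interpretation. The endpoint effect is real for an affected patient, but its size across the trial is unknown. The day counts assume nominal visit days and up-titration on the first permitted day, using unscheduled visits. The 1–5% range in the power illustration is an assumption, and no loss of power is claimed.

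**What to change.** Reconcile sections 4.1.4.1 and 4.1.4.2 so that a single rule governs up-titration after an interruption for a related adverse event after Visit 5, with a cross-reference making clear which section governs. Then check that the Appendix 10.3 schematic and the IRT settings match it. Which rule applies is a decision for the sponsor's clinical team, and this review takes no position on it. The cost is low: a protocol clarification and a check of the appendix and the IRT configuration.

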4.1.4.2 Rules for down-titration in case of intolerance to trial treatment

If a patient has an adverse event that the Investigator believes may be related to trial medication then the Investigator may either interrupt a patient's trial medication (re-start to follow the rules above (see [section 4.1.4.1](#)) or dose reduce the patient as described below. See [Appendix 10.3](#) for a schematic guidance on down-titration:

If the patient is on 1 mg TID or matching placebo the patient will be down-titrated to placebo matching 1 mg.

If the patient is on 2 mg TID or 3 mg TID (or corresponding matching placebo) and interrupts trial treatment

- less than 4 consecutive doses, then the patient will be down-titrated one level i.e.
 - 2 mg /placebo goes to 1 mg TID/ placebo.
 - 3 mg/ placebo goes to 2 mg TID/ placebo.
- 4 consecutive doses or more, then the patient will be down-titrated to 1 mg TID or placebo.

Dose-reduction must NOT be performed by taking less than the three daily doses or by splitting tablets so that a whole tablet isn't taken.

If the patient experiences a second adverse event that the Investigator believes is related and they have already had an interruption/ down-titration, then the patient should permanently discontinue trial treatment.

In case of persistent adverse events despite dose reduction, or severe effects at any dose, permanent treatment discontinuation should be considered.

Uptitration for patients who were down-titrated or interrupted for a related AE is not permitted.

